5.2 Secondary Endpoints

- 5.2.1 Poor bleeding score (binary) at 1, 2, 3, 4 weeks, 12 weeks, and 1 year after study enrollment defined as WHO Bleeding Scale ≥ 2 or Modified Buchanan Scale ≥ 3
- 5.2.2 Cumulative number of rescue therapies required during the first 12 weeks of treatment
- 5.2.3 Platelet response (binary), defined as ≥ 3 of 4 weeks with platelets $>50 \times 10^9/L$ during weeks 6-12 of therapy, but patient required a rescue treatment during weeks 1-2 of study
- 5.2.4 No further need for treatment (binary) after 12 weeks or 6 months of study
- 5.2.5 Treatment response (binary endpoints) at 1 year defined as:
 - **CR** is defined as platelet count $>/= 150 \times 10^9/L$
 - **Primary Remission** at 1 year is defined as CR at 1 year with no second-line agents required and $>/= 3$ months after discontinuing most recent platelet active medication
 - **Disease resolution** at 1 year is defined as CR at 1 year $>/= 3$ months after discontinuing most recent platelet active medication. May have received a second-line therapy, excluding rituximab or splenectomy.
 - **Disease stability** at 1 year is defined as platelets $>/= 50 \times 10^9/L$ but $<150 \times 10^9/L$ $>/= 3$ months after discontinuing most recent platelet active medication.
- 5.2.6 Number of 2nd-line therapies (defined in section 7.2.1) in weeks 13-52
- 5.2.7 Absolute change in percentage of CD4⁺25⁺Foxp3⁺ regulatory T cells from baseline at 12 weeks and 1 year
- 5.2.8 Absolute change in parent proxy-reported KIT overall scores from baseline to 1 week, 4 weeks, 12 weeks, and 1 year after study enrollment (see Appendix A2)
- 5.2.9 Total scale intensity ratings (continuous) from the Hockenberry Fatigue Scale-Parent (FS-P) at 1 week, 4 weeks, 12 weeks, and 1 year (see Appendix A2)
- 5.2.10 Serum iron, TIBC, transferrin saturation, ferritin, MCV, and hemoglobin at 12 weeks, 6 months, and 1 year after study enrollment
- 5.2.11 Safety evaluations as defined by:
 - Abnormal LFTs:
 - ALT $\geq 3x$ ULN in patients with normal baseline
 - ALT $\geq 3x$ baseline or $\geq 5x$ ULN (whichever is lower) in patients with abnormal baseline
 - ALT $\geq 3x$ ULN AND bilirubin $\geq 1.5 \times$ ULN ($>35\%$ direct)

- Incidence of adverse events (see section 9.1.6)
- Incidence of serious adverse events (see section 12.2)

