6.2 Exclusion Criteria

- Severe bleeding: Buchanan Overall Grade 4 or 5 bleeding (see Appendix A1), or severe bleeding requiring emergent treatment at the discretion of the provider. (e.g., intracranial hemorrhage, pulmonary hemorrhage, bleeding with ongoing need for pRBC transfusion)
- Prior treatment with TPO-RA (eltrombopag or romiplostim)
- Known secondary ITP (due to lupus, CVID, ALPS)
- Known HIV (or history of HIV positivity) or Hepatitis C (screening not required if no clinical suspicion)
- Evans Syndrome: positive direct Coombs with evidence of active hemolysis (elevated LDH or reticulocyte count not attributable to recent treatment or bleeding)
- Any Malignancy
- History of stem cell transplant or solid organ transplant
- AST or ALT >2x ULN
- Total bilirubin >1.5 × ULN
- Subjects with liver cirrhosis (as determined by the investigator)
- Creatinine >2.5 × upper limit of normal (ULN)
- Known active or uncontrolled infections not responding to appropriate therapy
- On anticoagulation or anti-platelet agents
- Known thrombophilic risk factors. *Exception: Subjects for whom the potential benefits of participating in the study outweigh the potential risks of thromboembolic events, as determined by the investigator.*
- Baseline ophthalmic problems that may potentiate cataract development
- Impaired cardiac function, such as:

- Known prolonged QTc, with corrected QTc >450 msec
 - Other clinically significant cardio-vascular disease (e.g., uncontrolled hypertension, history of labile hypertension),
 - History of known structural abnormalities (e.g. cardiomyopathy).
- History or current diagnosis of cardiac disease indicating significant risk of safety for patients participating in the study such as uncontrolled or significant cardiac disease, including any of the following:
 - Recent myocardial infarction (within last 6 months),
 - Uncontrolled congestive heart failure,
 - Unstable angina (within last 6 months),
 - Clinically significant (symptomatic) cardiac arrhythmias (e.g., sustained ventricular tachycardia, and clinically significant second or third degree AV block without a pacemaker.)
 - Long QT syndrome, family history of idiopathic sudden death, congenital long QT syndrome or additional risk factors for cardiac repolarization abnormality, as determined by the investigator.
- Known immediate or delayed hypersensitivity reaction to eltrombopag or its excipient.

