9.1.5 Bleeding Assessment

An in-person bleeding assessment will be performed at Baseline/Screening, at Study Visits Week 1, Week 4, Week 12, and 1 year, at unscheduled visits, and at early termination when applicable. Assessments will be performed via telehealth if associated study visit is performed remotely due to pandemic-related safety or research restrictions. A telephone bleeding assessment will be performed at weeks 2 and 3. (See Appendix for details of WHO Bleeding Scale and modified Buchanan Scale).

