16 STATISTICAL METHODS AND CONSIDERATIONS

Overview

This is a prospective, open label, randomized, two-arm, multi-center Phase 3 trial. Enrolled patients with newly diagnosed ITP are randomized at enrollment 2:1 to the experimental treatment arm (eltrombopag) and standard treatment arm (investigator's choice of 3 standard therapies); randomization will be stratified by patient's age at enrollment and up-front treatment status, with block size of 3. Each stratum will be limited to a maximum of 27 patients. Hence, the age distribution of the final accrued cohort may not be representative of the patient population. This is appropriate in the context of this study to ensure sufficient number of patients to study treatment effects in each age group. The primary objective is to determine

whether the proportion of patients with platelet response is greater in the experimental treatment arm compared to the standard therapy arm using a one-sided Cochran-Mantel-Haenszel (CMH) test at alpha=0.025 (see section 16.b).

Intent-to-Treat and Evaluability

For the primary objective, all randomized patients will be included in an intent-to-treat (ITT) analysis. Evaluability for the secondary and exploratory objectives: In the experimental treatment arm, patients will be considered evaluable if they receive at least one dose of eltrombopag. In the standard treatment arm, patients will be considered evaluable if they receive at least one dose of one of the standard of care treatments.

Statistical Analysis

a. Baseline Demographic and Clinical Characteristics

Patient demographic and clinical characteristics at study enrollment will be summarized using descriptive statistics, including frequencies and proportions for categorical measures, and means, medians, ranges, and standard errors for continuous measures.

b. Analysis of Primary Endpoint

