To address the primary objective, we will first test for normality of the distribution of the proportion of platelet responders. If the assumption of normality is upheld, a one-sided Cochran-Mantel-Haenszel (CMH) test, at alpha=0.025, will be used to compare the proportion of platelet responders between the two arms. If the normality assumption is violated, then a one-sided Fisher's exact test will be used. The monitoring boundaries and levels of significance for the interim and final analyses of the primary endpoint are detailed in Table 16A. If a monitoring boundary is crossed in an interim analysis, an independent Data Safety Monitoring Board (DSMB) will make a non-binding recommendation regarding trial conduct or potential closure. In the final analysis, we will reject the null hypothesis if the upper (efficacy) boundary z-value of 1.99302 is crossed; in that case, it will be reasonable to conclude that the rate of platelet response is significantly greater in patients treated with eltrombopag than standard first-line treatments. Otherwise, we will conclude that there is insufficient evidence to support superiority of eltrombopag over standard first-line treatments. All randomized patients will be analyzed in the ITT analysis.

Selection of platelet measurements for the determination of platelet response.

All platelet counts will be reported, and the four measurements closest in time to Weeks 6, 8, 10, and 12 will be selected for the determination of the primary endpoint. Within a sliding one-week window, only one measurement can be selected. Patients who have <3 platelet measurements due to missing data will be classified as non-responders.

c. Analysis of Secondary Endpoints

Analyses of all secondary endpoints will be performed in the subset of evaluable patients. To determine the effects of missing data, sensitivity analyses will be performed using two approaches: a) assuming missing at random; and, b) assuming missing not at random. For each secondary endpoint, the assumption of normality will be tested. If violated for binary endpoints, a Fisher's exact test will be used. If violated for continuous endpoints, a Wilcoxon rank-sum test will be used.

To address secondary objective 3.2.1, the Cochran-Mantel-Haenszel test will be used to compare the proportion of patients with poor WHO Bleeding Score and poor Modified Buchanan Score between the two arms.

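### The bleeding comparison for objective 3.2.1 makes no use of the baseline bleeding score, so it may lose precision and is exposed to chance baseline imbalance

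*Combined protocol and SAP*

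**What the plan says.** Section 5.2.1 makes poor bleeding a yes/no status, judged at six time points (weeks 1 to 4, week 12 and 1 year) and "defined as WHO Bleeding Scale ≥ 2 or Modified Buchanan Scale ≥ 3". Section 9.1.5 states that "An in-person bleeding assessment will be performed at Baseline/Screening, at Study Visits Week 1, Week 4, Week 12, and 1 year"; weeks 2 and 3 are assessed by telephone, and the schedule in section 9 (footnote 3) shows that the telephone assessment uses the modified Buchanan scale.

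For the analysis, section 16.c says that "the Cochran-Mantel-Haenszel test will be used to compare the proportion of patients with poor WHO Bleeding Score and poor Modified Buchanan Score". It names neither strata nor covariates. The fallback is unstratified: "If violated for binary endpoints, a Fisher's exact test will be used".

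Section 6.2 excludes "Severe bleeding: Buchanan Overall Grade 4 or 5 bleeding", along with severe bleeding needing emergent treatment. Section 16 says that "randomization will be stratified by patient's age at enrollment and up-front treatment status"; bleeding is not a factor. Section 16.c analyses Tregs, KIT and fatigue as change from baseline. No expected bleeding rate, effect size or power is given for 3.2.1.

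**The concern.** Buchanan overall grade 3 (overt mucosal bleeding, Appendix A1) and WHO grade 2 both count as poor scores, and neither is excluded as such. Some patients can therefore start the trial already in the outcome state. If they are more likely to score poorly at weeks 1 to 4, baseline status explains part of the outcome variation, and a test that leaves it out discards information already collected.

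Allocation is 2:1 with at most 54 controls, so a baseline difference of several points can arise by chance. Part of it would then appear as a treatment difference, in either direction. If adjustment were added only after such an imbalance had been seen, in an open-label trial, it would look data-driven.

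**Working it through.** **1. Stated figures.** There is none for 3.2.1. As a check on method, the primary power of 81.4% (98 vs 49, 75% vs 50%) was recomputed. The continuity-corrected calculation gives 80.8% (fixed design) or 80.7% (three looks), and the uncorrected pooled fixed-design one 85.4%. The stated figure is reproduced to within a point with the correction, and this issue does not affect it.

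**2. Chance imbalance.** Section 16.f gives 108 vs 54 randomized; the evaluable set for 3.2.1 is everyone dosed, so at most these numbers. For baseline poor-score prevalence p (assumed), the SD of the arm difference is √[p(1−p)(1/108 + 1/54)]:
- p = 20%: √(0.16 × 0.02778) = 6.7 points
- p = 30%: √(0.21 × 0.02778) = 7.6 points
- p = 40%: √(0.24 × 0.02778) = 8.2 points
- p = 50%: √(0.25 × 0.02778) = 8.3 points

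By the normal approximation, an absolute imbalance of 10 points or more has probability 13% at p = 20% and 23% at p = 50%. Simulation at 30% and 50% gave 19% to 26%.

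**3. How much carries over.** With no treatment effect, the expected shift in the later difference is the baseline imbalance times the difference in later risk by baseline status. Per SD of imbalance, with assumed later risks:
- 60% vs 15% (odds ratio 8.5), p = 40%: 0.45 × 8.2 = 3.7 points
- 40% vs 15% (odds ratio 3.8), p = 30%: 0.25 × 7.6 = 1.9 points
- 25% vs 15% (odds ratio 1.9), p = 30%: 0.10 × 7.6 = 0.8 points

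**4. Power.** Simulation of 162 patients in six strata (18:9 each), two-sided 0.05, complete data, 6,000 trials per scenario. Assumptions: baseline prevalence 30% or 50%; later poor-score rates of 40% vs 18%, or 25% vs 8%. CMH on the six randomization strata has about 82% to 86% power. Change from that, in points:

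| Baseline–outcome odds ratio | CMH by baseline status | CMH by six strata × baseline |
|---|---|---|
| 1–2 | −0.4 to +0.7 | −2.0 to −0.6 |
| 4 | +1.5 to +2.5 | −0.1 to +1.1 |
| 8 | +3.7 to +5.6 | +1.9 to +4.5 |
| 16 | +4.6 to +10.3 | +3.5 to +9.3 |

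A second set fixed the treatment odds ratio at 0.35, again with 162 patients. CMH by baseline status gained about 8 to 15 points at baseline odds ratios of 8.5 to 21, 2.6 at 3.8, and nothing at about 1.9 or with sparse events. Null rejection was 4.3% to 5.2%.

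**5. Error rates of the six-stratum CMH.** Overall null rejection is 4.4% to 5.4%. Among trials where the eltrombopag arm is at least 10 points worse at baseline, it is 5% to 7% at odds ratio 4 and 5% to 11% at odds ratio 8. In the same trials at odds ratio 4, its power is 70% to 73%, against 84% to 87% for CMH by baseline status.

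**6. Logistic alternative.** With 98 vs 49 patients and a treatment odds ratio of 0.35, power moved from 58% (six-stratum CMH) to 65% at risks of 60% vs 15%, and from 54% to 56% at 40% vs 15%. With an overall event rate of about 5% (162 patients), the likelihood-ratio test rejected a true null 7.5% of the time, against 4.0% for CMH, and about 24% of null fits had a diverging coefficient.

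Monte Carlo error in steps 4 and 5 is about 0.5 points, or 1 to 2 points for figures conditional on imbalance.

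**The case against.** The strongest reply is that the planned test is valid. Randomization protects its overall type I error, which simulation confirms, and chance imbalance is already allowed for in that error rate. This stands: the case for adjustment rests on precision and on the error rate given the imbalance actually seen.

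Second, every bleeding rate and association above is assumed. A reader might infer that the planned analysis definitely loses power. The documents do not support that, because they give no link between baseline and later bleeding; with a weak link there is nothing to gain. This also stands.

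Third, the contrast with KIT and Tregs is limited. Those endpoints are defined as changes, whereas 5.2.1 is a status, and CMH is the plan's usual test for binary secondary endpoints. The contrast shows only that baseline data are used elsewhere.

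Fourth, adjustment can do harm if done badly. Crossing baseline status with all six strata loses power when the link is weak, and logistic regression is unreliable with few events. Section 2.2 expects most patients to resolve within a year, so late poor scores may be rare. This limits the form of the fix but does not remove the point.

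A reader might also infer that section 16 makes no use of bleeding seen at unscheduled visits. That goes too far: the exploratory response and loss-of-response endpoints (5.3.1, analysed in 16.d) include bleeding, and nothing confines them to scheduled visits.

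**Conclusion.** The point holds as a matter of precision and prespecification. The baseline score is collected, patients may enter with a poor score, and neither the randomization nor the 3.2.1 analysis accounts for it. Under the assumed rates, CMH by baseline status gains about nothing at a baseline odds ratio of 1 to 2, about 2 points at 4, and roughly 4 to 15 points at 8 or more. The spread at the top reflects different assumed rates and starting power. The six-stratum comparator is itself an assumption, because the plan names no CMH strata for 3.2.1.

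It would be wrong to conclude that the planned test is invalid or that the primary result is at risk. The type I error is kept overall, and only one secondary objective is concerned.

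**What to change.** In 16.c, replace the 3.2.1 sentence with a CMH test stratified by baseline poor-score status, reporting a stratified risk difference with 95% CI at each time point. Define baseline status on the same scale as the outcome at that visit, which means modified Buchanan only at weeks 2 and 3.

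At the early visits, where events are sufficient, a logistic model with treatment, baseline status, age group and up-front status may be prespecified instead. Do not cross baseline status with all six strata, and do not rely on standard logistic regression at 12 weeks or 1 year if events are sparse.

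Any summary that adds unscheduled assessments should be omitted or labelled descriptive. The trial is open label and monitoring differs by arm, so the frequency of visits, and with it the chance of recording a poor score, may differ too.

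The cost is one changed analysis term and SAP wording, with no new data. If baseline bleeding is weakly prognostic, expect little or no gain and possibly a loss of about half a point of power. The change should be made before comparative bleeding data are reviewed.

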3.2 Secondary Objectives

- 3.2.1 To compare the proportion of patients with poor bleeding scores (WHO Bleeding Scale \geq 2 or Modified Buchanan Score \geq 3) at 1, 2, 3, 4, 12 weeks and 1 year in patients with newly diagnosed ITP treated with eltrombopag vs. standard first-line agents
- 3.2.2 To compare the cumulative number of rescue therapies (defined in section 8.4) needed during the first 12 weeks of treatment for patients with newly diagnosed ITP treated with eltrombopag vs. those treated with standard first-line agents
- 3.2.3 To compare platelet response during weeks 6-12 of study in patients treated with eltrombopag vs standard first line agents who required a rescue treatment during weeks 1-2 of study
- 3.2.4 To compare the proportion of patients who do not need ongoing treatment at 12 weeks and 6 months for patients with newly diagnosed ITP treated with eltrombopag vs. those treated with standard first-line agents
- 3.2.5 To compare the proportion of patients with a treatment response (4 binary endpoints (section 5.2.5)) at one year after study enrollment in patients with newly diagnosed ITP treated with eltrombopag vs. those treated with standard first-line agents
- 3.2.6 To compare the number of 2nd-line therapies (defined in section 7.2.1) used in weeks 13-52 for patients with newly diagnosed with ITP treated with eltrombopag vs. those treated with standard first-line agents
- 3.2.7 To compare the absolute change in percentage of CD4 $^{+}$ 25 $^{+}$ Foxp3 $^{+}$ regulatory T cells (Tregs) a) from baseline to 12 weeks; and b) from baseline to 1 year, in patients with newly diagnosed ITP treated with eltrombopag vs. those treated with standard first-line agents
- 3.2.8 To compare change in Health Related Quality of Life (HRQoL) from a) baseline to 1 week, b) baseline to 4 weeks, c) baseline to 12 weeks, and, d) baseline to 1 year, as measured by the parent-proxy report of the Kids ITP tools (KIT) and Global Change Scale for patients with newly diagnosed ITP treated with eltrombopag vs. those treated with standard first-line agents
- 3.2.9 To compare fatigue at 1 week, 4 weeks, 12 weeks, and 1 year as measured by the parent-proxy report of the Hockenberry Fatigue Scale-Parent (FS-P)

for patients with newly diagnosed ITP treated with eltrombopag vs. those treated with standard first-line agents

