To address secondary objective 3.2.2, an ANCOVA model will be used to compare the number of rescue therapies between the two arms.

To address secondary objective 3.2.3, the observed proportion and 95% confidence interval of platelet responders will be calculated in the subset of patients who required a rescue treatment during weeks 1-2 of the study.

To address secondary objective 3.2.4, the Cochran-Mantel-Haenszel test will be used to compare the proportion of patients who do not need ongoing treatment at 12 weeks and 6 months between the two arms.

To address secondary objective 3.2.5, the Cochran-Mantel-Haenszel test will be used to compare the proportion of patients with a treatment response at one year between the two arms.

To address secondary objective 3.2.6, an ANCOVA model will be used to compare the number of 2nd-line therapies between the two arms

To address secondary objective 3.2.7, an ANCOVA model will be used to compare the absolute change from baseline in percentage of regulatory T cells at 12 weeks and 1 year between the two arms

To address secondary objective 3.2.8, KIT scores will be calculated as per the methods described in Klaassen et al.²⁸ Spaghetti plots will be used to visualize the KIT scores over time per patient by treatment arm. An ANCOVA model will be used to compare the absolute change from baseline in KIT overall score at 1 week, 4 weeks, 12 weeks, and 1 year between the two arms. An ANCOVA model will be used to compare the Change Scale score at 1 week, 4 weeks, 12 weeks, and 1 year between the two arms.

To address secondary objective 3.2.9, fatigue scores will be calculated as per the methods described in Hockenberry et al.²⁹ All measures will be rescaled from 0 (no fatigue) to 100 (high fatigue) for consistency in scoring. Spaghetti plots will be used to visualize the fatigue scores over time per patient by treatment arm. The PROMIS tired question: “My child (I) got tired easily never to almost always” will be used as an anchor with severe fatigue defined as “often” or “almost always” with moderate fatigue being “sometimes”. An ANCOVA model will be used to compare the absolute change from baseline in fatigue at 1 week, 4 weeks, 12 weeks, and 1 year between the two arms.

To address secondary objective 3.2.10, an ANCOVA model will be used to compare iron indices at 12 weeks, 6 months, and 1 year between the two arms

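### Objective 3.2.3 promises a between-arm comparison in early-rescued patients, but Section 16.c plans only a proportion and interval, with no split by arm and no contrast

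*Combined protocol and SAP*

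**What the plan says.** Objective 3.2.3 (Section 3.2) is "To compare platelet response during weeks 6-12 of study in patients treated with eltrombopag vs standard first line agents who required a rescue treatment" in weeks 1-2. Endpoint 5.2.3 is a binary platelet response over weeks 6-12 that carries the same condition: "but patient required a rescue treatment during weeks 1-2 of study".

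For this objective Section 16.c states that the responder proportion and its 95% confidence interval "will be calculated in the subset of patients who required a rescue treatment during weeks 1-2 of the study". It does not mention arms, a difference or a test. The next objective, 3.2.4, is treated differently: a Cochran-Mantel-Haenszel (CMH) test is named "to compare the proportion of patients who do not need ongoing treatment at 12 weeks and 6 months between the two arms". Objectives 3.2.1 and 3.2.5 also receive a between-arm CMH test.

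Four other provisions bear on the point:

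- Section 16.c has a general rule, "For each secondary endpoint, the assumption of normality will be tested", with Fisher's exact test for binary endpoints if the assumption fails.
- Section 5.1 makes any patient who needs rescue in the first 12 weeks a primary non-responder.
- Section 8.3 leaves the use and choice of rescue to the investigator.
- Section 16 describes an open-label trial and adds: "Enrolled patients with newly diagnosed ITP are randomized at enrollment 2:1 to the experimental treatment arm (eltrombopag) and standard treatment arm".

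**The concern.** The objective and its analysis do not match. A single proportion with an interval, not stated to be by arm, says nothing about eltrombopag against standard therapy. If the analysis is run as written, objective 3.2.3 will have no answer, or the missing contrast will be chosen after the data are seen.

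Adding a test inside the subset would not fully repair this. Patients enter the subset through an event after randomisation, decided by investigators who know the arm. A difference found there could reflect who was rescued in each arm as much as what the treatments did.

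**Working it through.** **1. Text against text.** The objective asks for a comparison of arms. The analysis gives a proportion and a 95% interval in the subset. The general normality rule does not fill the gap, because it only replaces a named test with another and 3.2.3 names none.

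**2. Which responder definition applies.** Section 16.c refers to platelet responders. Under Section 5.1, rescue at any time in the first 12 weeks makes a patient a non-responder, so on that definition the proportion in this subset is 0% by construction. Endpoint 5.2.3 must be the one intended, but 16.c does not cite it, and 5.2.3 does not say how a further rescue in weeks 3-12 is classified.

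**3. Selection.** Early rescue may mean different things by arm. Eltrombopag is given daily, and apart from holding for thrombocytosis its dose is adjusted only after two weeks on the prior dose (Section 8.2.2.1). Standard therapy is a single dose or a four-day course (Section 8.2.1), and a repeat after a waning response counts as rescue (Section 8.3).

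An illustration with assumed numbers and no treatment effect: half the patients have good prognosis (70% respond) and half poor (30% respond). Response among the rescued is (0.7g + 0.3b)/(g + b), where g and b are the rescue rates in the two groups.

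- Both arms g = 0.10, b = 0.30: 40% in each arm, so no bias.
- One arm g = 0.30, b = 0.40: 0.33/0.70 = 47%, against 40%.
- One arm g = 0.05, b = 0.35: 0.14/0.40 = 35%, against 40%.

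Spurious differences can therefore arise in either direction.

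**4. Upper limit on the subset.** The plan states no figure for 3.2.3, so there is none to reproduce. The inputs come from the primary power calculation: 98 and 49 informative patients with 75% and 50% response. (Its 81.4% power is close to the 80.8% obtained with a continuity correction; without one the result is 85.4%.) Rescue implies primary non-response, so the rescued cannot outnumber the non-responders:

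- eltrombopag: 98 × 0.25 = 24.5
- standard: 49 × 0.50 = 24.5
- total: 49, or 49/162 = 30% of those randomised

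This covers all of weeks 1-12, so the weeks 1-2 subset is the same size or smaller. Some of the roughly 15 early withdrawals might also have been rescued, but they would have no week 6-12 counts.

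**5. Precision.** The early-rescue rate is an assumption. The table applies one rate to both arms (108 and 54 randomised), with 75% and 50% response assumed in the subset. The half-width of the difference is 1.96 × √(0.1875/n_E + 0.25/n_S).

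| Assumed early rescue | n_E vs n_S | 95% half-width of difference |
|---|---|---|
| 5% | 5 vs 3 | 68 points |
| 10% | 11 vs 5 | 51 points |
| 20% | 22 vs 11 | 35 points |
| 30% | 32 vs 16 | 29 points |
| 40% | 43 vs 22 | 25 points |

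The formula is rough in the smallest rows. The 30% and 40% rows put more than 24.5 eltrombopag patients in the subset, so they exceed the limit in step 4 and show only the generous end. At that limit, 24 vs 24, the half-width is 1.96 × √(0.4375/24) = 26 points.

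**6. Power, if a test were added.** For 75% vs 50% at one-sided 0.025, 80% power needs 129 rescued patients at 2:1 (86 and 43) or 116 at 1:1. At 24 vs 24, power is about 43% (pooled normal approximation) or 34% (Fisher's exact test).

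**The case against.** The best defence is that description is the restrained choice. If a contrast in this subset is not protected by randomisation, a proportion with an interval and no p-value avoids a misleading test. No superiority claim rests on 3.2.3, and the primary analysis is untouched. This stands as a reason not to make a subset test the main repair. It does not explain why the objective says compare, or why the proportion is not given by arm.

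A reader might also infer three stronger points that the documents do not support:

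- *That 3.2.3 really asks about the effect in all patients once early rescue is allowed.* Objective 3.2.3 and endpoint 5.2.3 both restrict the question to rescued patients. The all-patient question is a useful addition, but the plan does not pose it.
- *That rescued patients in the two arms are known to differ.* Open-label assignment and discretionary rescue create a risk. The documents contain no data showing that selection occurs or how large it would be.
- *That the subset has a known size.* No early-rescue rate is given. That it will be small is an inference from the plan's response assumptions, and any single rate would be a guess.

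**Conclusion.** The point holds as a mismatch between an objective and its analysis, with an unclear responder definition. As written, Section 16.c does not answer objective 3.2.3. Any contrast within the subset would be non-randomised and imprecise: no better than about 26 points either side under the plan's own response assumptions, and 68 to 25 points over assumed rescue rates of 5% to 40%. These figures assume 75% and 50% response in the subset; the table also assumes equal rescue rates in the two arms. The consequence is limited to one secondary objective.

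**What to change.** In Section 16.c, for objective 3.2.3:

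- report n, proportion and 95% interval separately by arm, with the difference and its interval labelled non-randomised and descriptive;
- cite the 5.2.3 definition of response in place of the unqualified term, and state how rescue in weeks 3-12 is counted for this analysis;
- add a supplementary stratified CMH comparison in all randomised patients of at least 3 of 4 counts above 50 × 10⁹/L at weeks 6-12, with rescue in weeks 1-2 not counted as failure and later rescue counted as failure.

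With 108 and 54 patients and 50% response in each arm, the supplementary difference would have a half-width of 1.96 × √(0.25/108 + 0.25/54) = 16 points. It estimates a different quantity, so this is not a like-for-like gain over the subset.

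The cost is mainly wording. The supplementary analysis adds an estimand and departs from the evaluable set that Section 16 prescribes for secondary endpoints; both should be stated. If the sponsor prefers description alone, objective 3.2.3 should be reworded to say so. Any change to the text of the objective or endpoint needs a protocol amendment with ethics approval (Section 18.a). No new data are needed: the Section 9 schedule already collects rescue forms and all week 5-12 platelet counts, and assessments continue after treatment stops.
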